#### Rationale

As of March 20, 2020, the novel 2019-coronavirus has infected nearly 250,000 people resulting in over 10,000 deaths. There is no known treatment for this disease. Among the subset of patients who develop critical illness, evidence points towards the development of a cytokine storm syndrome that is similar to what is observed in secondary hemophagocytic lymphhistiocytosis (sHLH). Clinical and laboratory features of sHLH include high fevers, elevated ferritin, elevated triglycerides, low fibrinogen, and cytopenias. About half of the patients with sHLH develop ARDS which carries a high mortality (1). In China, hypercytokinemia was observed in patients with severe COVID disease and one study published online associated elevations in ferritin and IL-6 with greater mortality risk in these patients (6). It is reasonable to postulate that the pulmonary involvement may be the result of unchecked hyperinflammation, and that there may be a benefit to immunosuppressive, specifically, anti-cytokine therapies. Currently a multicenter randomized trial to evaluate the IL-6 receptor blocker tocilizumab is rolling out in China. Vitaeris Inc manufactures a direct IL 6 inhibitor, clazakizumab, which is currently under phase 3 investigations for patients with chronic active antibody mediated rejection after kidney transplantation. Recognizing, based on its mechanism of action, clazakizumab is hypothesized to have benefit for patients with life-threatening COVID-disease, Vitaeris is willing to provide drug for this investigator initiated trial for use in patients who are at greatest risk of dying from COVID-19 disease. This study is a prospective, randomized, double-blind, placebo-controlled trial of clazakizumab to prevent death from respiratory and multi-organ failure in COVID-19 disease. An under recognized comorbidity in SARS-CoV-2 infected patients is acute kidney injury (AKI) occurring in up to 30% of critically ill patients, and contributing to fluid retention, worsening oxygenation, and the need for renal replacement therapy (RRT). While multiple etiologies may be at play, the effects of systemic and possibly local inflammation are highly likely to be significant contributing factors. Improving renal function via IL-6 inhibition would be a substantial clinical benefit.

## Name and Description of the Investigational Agent

Investigational agent: clazakizumab Supplier of clazakizumab: Vitaeris Inc, Vancouver, BC, Canada Manufacturer: Ajinomoto Althea Bio-Pharma, Inc, San Diego CA, USA

## **Objectives and Purpose**

## Primary Objective

The primary objective is to assess the safety of clazakizumab treatment in COVID-19 infected patients with respiratory failure due to hyperinflammation related to cytokine storm. Secondary Objectives

The secondary objectives are to assess efficacy by evaluating the incidence and duration of mechanical ventilation, the length of ICU stay, severity and duration of acute kidney injury (AKI) and patient survival in patients who receive IP at two different doses versus placebo.

## **Study Design and Endpoints**

This is a randomized, double-blind, placebo-controlled, design. We propose the administration of an investigational drug in patients with high predicted short-term mortality secondary to COVID-19 disease. 30 Patients will be randomly assigned in a 1:1 ratio to two study arms that will receive clazakizumab at a dose of 25 mg or placebo.

Primary Study Endpoints

The primary endpoint is patient safety assessed by serious adverse events associated with clazakizumab or placebo.

Secondary Study Endpoints

The secondary endpoints are: incidence of intubation, time to extubation, length of ICU stay, trend in C-reactive protein, severity of AKI, need for RRT, duration of RRT, and patient survival at 28 and 60 days.

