## Participant Withdrawal or Termination

The predicted mortality rate for patients with COVID-19 and ARDS is in excess of 50% (7). As such we anticipate there will be mortality amongst some of the participants. Death will constitute withdrawal from the trial. Otherwise we would not anticipate premature withdrawal from the study as the patients are expected to remain hospitalized (likely in an ICU setting) for the entire duration of the 14-day period where study specific data are collected. If the patient is discharged before day 28 survival status will be obtained by patient lookup in the electronic medical record. For discharged patients in whom there is no definitive record documenting patient status (alive or dead) after 28 days have elapsed, the study team will contact the patient or patient's family by phone to assess patient survival and to assess for the occurrence of any interim AEs/SAEs. At end of study (day 60), a phone call will also take place to assess patient survival and again asses for interim AEs/SAEs. The IP administration will occur over a maximum of 3 days following enrollment. Study specific laboratory tests will be performed in the first two weeks and if a patient (or consent designee should the patient lack capacity) wishes to withdraw from participation and refuse these laboratory studies, they will be free to do so.

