## Statistical and Analytical Plans (SAP)

Descriptive statistics for the safety endpoints will be used. With 10 patients, the 95% confidence interval (CI) around the rate of SAEs will be no more than 0.62 units wide. With 20 patients (combining the low dose and high-dose groups), the 95% CI will be no more than 0.46 units wide. Regarding the secondary outcome of patient survival, too little is known about the expected clinical behavior of these patients to make meaningful projections about expected changes in mortality given drug efficacy. Data will be analyzed across three sites: NYU, where this protocol originated; Columbia/NYP; and Johns Hopkins.

The first 80 patients at NYU were enrolled in the three-arm study using a 1:1:1 ratio. Following the DSMB's recommendation, additional NYU patients (expected to be 10) will be randomized in a 1:1 ratio to placebo or 25 mg clazakizumab. Columbia/NYP and Johns Hopkins will each enroll 30 patients in a 1:1 randomization ratio, with 15 patients each on clazakizumab 25mg and placebo. At these other sites, with 15 patients, the 95% confidence interval (CI) around the rate of SAEs will be no more than 0.52 units wide. The total planned enrollment of 150 subjects across these three sites will considerably increase the power to detect treatment effects. The table below summarizes approximate power for the projected sample size in the placebo and 25 mg clazakizumab groups (N=60 in each arm) to detect various reductions in mortality from the expected 50% rate in the placebo group, for various levels of Type I error (alpha) assuming use of a two-sided test. For example, we have approximately 82% power

to detect a reduction in the mortality rate of 50%, from 0.5 in the placebo group to 0.25 in the treated group, assuming 60 patients per group, at the usual Type I error rate of 0.05.

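### No rule is stated for death before intubation or before RRT, so the crude incidences of both endpoints are biased against a drug that improves survival

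*Combined protocol and SAP*

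**What the plan says.** The Study Design and Endpoints section lists the secondary endpoints: "The secondary endpoints are: incidence of intubation, time to extubation, length of ICU stay, trend in C-reactive protein, severity of AKI, need for RRT". The same list ends with "patient survival at 28 and 60 days" as a separate item. For intubation and RRT there is no time window, denominator or rule for death.

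These are efficacy measures. Under Objectives and Purpose, "The secondary objectives are to assess efficacy by evaluating the incidence and duration of mechanical ventilation" opens a list that also covers ICU stay, AKI and survival.

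High mortality is expected. Participant Withdrawal or Termination says "The predicted mortality rate for patients with COVID-19 and ARDS is in excess of 50" per cent, and then "Death will constitute withdrawal from the trial". It does not say what that means for any endpoint.

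The SAP plans descriptive statistics for safety and gives power "to detect a reduction in the mortality rate of 50%, from 0.5 in the placebo group to 0.25 in the treated group". It gives no method for intubation or RRT: no composite with death, no event-free survival and no competing-risk analysis.

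The Study Procedures section already collects the dates of intubation, of starting RRT and of death.

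**The concern.** Death before the event prevents the event from being seen. If intubations and RRT starts are simply counted over all patients, someone who dies without either is recorded as not having needed it, which is the favourable result. When both arms lose the same share of patients this way, the comparison is little disturbed. Here the plan's own power scenario halves mortality, so the share would differ by arm. Patients kept alive by the drug remain exposed to intubation and RRT, and some will have them.

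At stake is the efficacy reading of two named endpoints. A modest real respiratory or renal benefit could be hidden by a survival benefit, and with enough deaths before the event it could appear as harm. With no rule fixed in advance, the pooled three-site data could be handled in several ways, and the choice could be made after the results are known.

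**Working it through.** **The plan's own figure.** The only efficacy figure is about 82% power for mortality of 0.50 versus 0.25, with 60 per arm and two-sided alpha 0.05. With pooled variance (mean proportion 0.375):

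Φ[(0.25·√60 − 1.96·√(2·0.375·0.625)) / √(0.5·0.5 + 0.25·0.75)] = 0.816.

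It reproduces. No figure is given for intubation or RRT.

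**Inputs**
- Mortality of 50% on placebo and 25% on drug: SAP.
- Hazard ratio for death without the event: ln(0.75)/ln(0.50) = 0.415. This assumes that the SAP's mortality effect applies to deaths without the event.
- Placebo event incidence pe and placebo share dying without the event pd: not in the documents, so varied.
- Constant cause-specific hazards: assumption.

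**Formula.** Placebo total cumulative hazard H = −ln(1 − pe − pd). The event part is E = H·pe/(pe + pd) and the death part is D = H·pd/(pe + pd). On drug, with event hazard ratio θ, the event incidence is θE/(θE + 0.415D) × [1 − exp(−θE − 0.415D)]. The composite is the bracketed term.

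**Worked case, no drug effect on the event (θ = 1), pe = 30%, pd = 20%.** H = −ln(0.50) = 0.693, E = 0.416, D = 0.277. On drug the death part is 0.277 × 0.415 = 0.115, so the total is 0.531. Incidence = (0.416/0.531) × (1 − e^−0.531) = 0.783 × 0.412 = 32.3%.

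**Range with θ = 1, pe = 30%**

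| Placebo death without event | Event on drug | Composite, placebo to drug | θ at which the arms look equal |
|---|---|---|---|
| 10% | 31.1% | 40.0% to 35.3% | 0.96 |
| 20% | 32.3% | 50.0% to 41.2% | 0.91 |
| 35% | 34.6% | 65.0% to 51.3% | 0.84 |

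The last column is the θ that makes the drug-arm incidence equal to pe. It corresponds to hidden hazard reductions of about 4%, 9% and 16%.

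For pe = 15% and the same three shares, the drug arm shows 15.5%, 16.1% and 17.1%. For pe = 50% and shares of 5%, 20% and 35%, it shows 50.9%, 54.3% and 59.1%.

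**Does a real 15% reduction (θ = 0.85) change sign?** With pe = 32%:

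| Placebo death without event | Event on drug |
|---|---|
| 10% | 29.0% |
| 20% | 30.2% |
| 25% | 30.9% |
| 30% | 31.7% |
| 39.5% | 33.4% |

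Solving for equality with pe puts the crossing at about 32% dying without the event (33% for pe = 30%). It moves with the incidence: about 39% for pe = 15% and 25% for pe = 50%.

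**An extreme case, for RRT by Day 28.** Let all mortality act as death without RRT. The daily hazards are −ln(0.50)/28 = 0.02476 on placebo and −ln(0.75)/28 = 0.01027 on drug. With a placebo RRT hazard of 0.02 per day:
- Placebo incidence = 0.02/0.04476 × (1 − e^(−28 × 0.04476)) = 31.9%, with 39.5% dying without RRT.
- On drug with no renal effect, the incidence is 37.8% and the composite goes from 71.4% to 57.2%.
- On drug with a 15% hazard reduction, the incidence is 33.3% and the composite goes from 71.4% to 53.4%.

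At 1% and 3% per day, the incidences with the 15% reduction are 17.9% versus 18.5% and 43.0% versus 45.1%. These cases imply that 44.3% and 35.5% of placebo patients die without RRT.

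**The case against.** **The protocol does not say that such a death is a success.** This stands. A reader might infer a scoring rule from the endpoint names, but none is written. Treating death as withdrawal could also mean censoring or exclusion. Those readings leave the comparison dependent on mortality too, so what is established is a missing rule.

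**Reversal needs an extreme share of deaths before the event.** This also stands. A reader might infer that a real 15% reduction would generally look like harm. The three constant-hazard cases all show it, but only because 35% to 44% of placebo patients die without RRT in them, which is 71% to 89% of a 50% mortality. If most deaths follow RRT or intubation, the direction stays correct and the effect is only attenuated. No figure in the documents sets this share.

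**The shifts are small against noise.** Near 32% incidence and 60 per arm, the standard error of the difference is √(0.319·0.681/60 + 0.333·0.667/60), about 8.6 points. The reversals above are 0.6 to 2.1 points. That limits the practical harm, but the bias is systematic and larger samples do not remove it.

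**A composite has its own bias.** With no renal effect it still falls from 71.4% to 57.2% through mortality alone. This is a sound reason not to substitute it for the existing endpoints.

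**Survival is reported separately, and the primary endpoint is safety.** Both are true. They limit the consequence but do not define the two endpoints.

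**Conclusion.** The concern holds as a missing rule with a predictable direction of bias. If events are counted as named and the drug improves survival, both crude incidences are pushed against it. At a 30% placebo incidence with no effect on the event, the push is about 1, 2 or 5 points when 10%, 20% or 35% of placebo patients die without the event. Modest benefits can be masked. At placebo incidences near 30%, a 15% hazard reduction changes sign only when more than about 30% die without the event.

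This rests on the SAP's 50% versus 25% mortality, on applying that effect to deaths without the event, on constant hazards, and on assumed incidences and shares. For intubation the share is especially uncertain, because patients already ventilated may be enrolled and cannot die before intubation. The documents do not support saying that the plan scores death as a success, or that reversal is the expected result. The primary safety endpoint is unaffected. The point should be corrected, but it does not threaten the trial's main result.

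**What to change.** In the Study Design and Endpoints section and the SAP:

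1. Keep incidence of intubation and need for RRT. Define each in patients at risk at baseline (not already ventilated, or not already on RRT), by Day 28 and by Day 60 to match the survival endpoint, and state how death before the event is handled.
2. Add intubation or death, and new RRT or death, by the same days and in the same patients, as the between-arm comparisons that are robust to death.
3. Beside each composite, report the event and death without the event separately, with cumulative incidence curves that treat death as a competing event.
4. State that the composite alone will not be read as evidence of a renal or respiratory effect.

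The cost is wording in the protocol and SAP. The dates needed are already collected, so there are no new data or visits. The drawback is that each composite overlaps with survival and can move through mortality alone, which is why the components must be shown. Restricting to patients at risk also leaves fewer than 60 per arm wherever some are already ventilated or on RRT.

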(This visit pertains only to subjects who remain inpatient at this time. If discharged, we will collect available data from the medical record.)

Day 14 laboratory studies

Collection of clinical data (vital signs, laboratory results, hemodynamic parameters, respiratory parameters, RRT)

Day 28 +/- 3:

Phone visit for documentation of survival status and assessment of interval AE/SAEs Collection of clinical data (laboratory results indicating kidney function, RRT)

Day 60 +/- 5:

Phone visit for documentation of survival status and assessment of interval AE/SAEs Collection of clinical data (laboratory results indicating kidney function, RRT)

Additional clinical data to be collected:

- Date of symptom onset
- Date of intubation (if performed)
- Date of extubation (if performed)
- Date of tracheostomy (if performed)
- Dates of initiation/discontinuation and type of renal replacement (if performed)

- Use and duration of prone positioning (if performed)
- Date of ICU discharge (if occurs)
- Date of hospital discharge (if occurs)
- Date of death (if occurs)

Additional data to be collected if testing becomes available during the conduct of this trial: Assessment of SARS-CoV-2 viral load by quantitative RT-PCR in blood. This would be tested at enrollment and on day7 if this assay becomes available and able to be performed in the New York Presbyterian Hospital CUIMC Clinical Laboratory.

Should the patient choose to withdraw from the study before the 60 day study duration has elapsed, the patient's choice to withdraw will be documented. The patient will be followed by the medical record to collect clinical data obtained for standard clinical care as pertains to the study outcomes.

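### Time to extubation is not tied to being alive or staying off the ventilator, and the data list cannot reliably identify failed extubations

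*Combined protocol and SAP*

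**What the plan says.** The secondary endpoints in Study Design and Endpoints begin with "incidence of intubation, time to extubation, length of ICU stay". Time to extubation appears by name only: there is no event definition, no time origin, no condition that the patient is alive and no period that must be spent off the ventilator. Its purpose is clear from the secondary objectives under Objectives and Purpose, which assess efficacy by "evaluating the incidence and duration of mechanical ventilation".

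The additional clinical data listed at the end of the schedule of events include four relevant single items:

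- "Date of intubation (if performed")
- "Date of extubation (if performed")
- "Date of tracheostomy (if performed")
- "Date of death (if occurs")

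No repeat intubation or extubation date is listed, and no reason for extubation. Nothing says how a tracheostomy enters the endpoint.

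The only rule on death is in Participant Withdrawal or Termination: "Death will constitute withdrawal from the trial". The SAP gives no analysis method for time to extubation. Its one worked power example concerns mortality, a fall "from 0.5 in the placebo group to 0.25 in the treated group".

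**The concern.** A shorter time to extubation will be read as benefit, so the event has to mean recovery from the need for ventilation. As the endpoint and data list stand, two kinds of extubation that are not recovery would also supply a date: removal of the tube when life support is withdrawn, and an extubation followed by reintubation. No rule removes either.

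This matters more here than in a low-mortality setting, because the trial expects about half of placebo patients to die. The arm with more deaths has more opportunity for end-of-life extubation. If the drug lowers mortality, the placebo arm would collect more of these events, and the recorded difference between arms would be smaller than the true difference in recovery. If the drug raises mortality, the same mechanism would partly hide the harm, which is unwelcome in a trial whose primary objective is safety.

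Treating death as withdrawal does not address this. The extubation precedes the death, so the event has already been counted when the withdrawal occurs.

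**Working it through.** **1. The plan's own figure.** Inputs from the SAP: mortality 0.50 versus 0.25, 60 per arm, two-sided alpha 0.05, stated power about 82%. With pooled variance under the null,

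power = Φ[(|d| − 1.96·√(2p̄(1−p̄)/n)) / √((p₁(1−p₁)+p₂(1−p₂))/n)].

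Here d = 0.25 and p̄ = 0.375. The first root is √(2×0.375×0.625/60) = 0.0884 and the second is √((0.25+0.1875)/60) = 0.0854. Power = Φ[(0.25 − 0.1732)/0.0854] = 0.816. The stated figure reproduces. It concerns mortality and plays no part in the problem below.

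**2. Illustration for extubation.** The documents give no rate of extubation, end-of-life extubation or reintubation, so these are assumptions:

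- mortality m = 0.50 (placebo) and 0.25 (25 mg), 60 per arm, as in the SAP example;
- all patients ventilated;
- v = 0.15 per arm alive but still ventilated;
- f = share of deaths preceded by an extubation at withdrawal of life support, equal in both arms.

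Truly liberated: 1 − m − v. That is 0.35 versus 0.60, a difference of 25 points.

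Recorded as extubated: 1 − m − v + f·m. The difference is (0.50 − 0.25)(1 − f).

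| f | placebo | 25 mg | difference | power, 60 per arm |
|---|---|---|---|---|
| 0 | 35% | 60% | 25 points | 79% |
| 0.1 | 40% | 62.5% | 22.5 points | 70% |
| 0.2 | 45% | 65% | 20 points | 60% |
| 0.4 | 55% | 70% | 15 points | 40% |
| 0.6 | 65% | 75% | 10 points | 22% |

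The power column uses the formula in step 1 as a yardstick. The plan specifies no such test for this endpoint.

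**3. Adding failed extubations.** Suppose also that a share r = 0.15 of the remaining patients who do not recover has a failed extubation. Recorded = 1 − m − v + f·m + r[(1−f)m + v], and the difference becomes 0.25(1−f)(1−r):

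- f = 0: 0.25 × 0.85 = 21.25 points, power 65%;
- f = 0.2: 0.25 × 0.80 × 0.85 = 17.0 points, power 48%;
- f = 0.4: 0.25 × 0.60 × 0.85 = 12.75 points, power 32%.

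**4. When the arms do not differ, or differ the other way.**

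- Mortality 0.50 in both arms: the difference is 0 for every f. There is nothing to dilute.
- Mortality 0.60 on drug and 0.50 on placebo: a true deficit of 10 points is recorded as 10 × 0.8 = 8 points at f = 0.2 and 10 × 0.6 = 6 points at f = 0.4.

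**5. A second set of assumptions.** Take ventilated mortality of 60% versus 30%, every survivor liberated and 36 ventilated per arm, none of which is in the documents. The true difference is 30 points (power 73%). It is recorded as 30 × 0.8 = 24 points at f = 0.2 (57%), 30 × 0.6 = 18 at 0.4 (40%) and 30 × 0.4 = 12 at 0.6 (26%). The direction and rough size match step 2.

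**The case against.** The strongest reply is that the documents nowhere say that any recorded extubation is the event, that the first date is used, or that extubation equals recovery. The secondary objective speaks of duration of ventilation, which fits total ventilated time just as well. That is fair. A reader might infer that the plan has chosen to count every extubation; it has not. It is silent, and the point rests on what the silence permits.

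Second, a reader might conclude that the treatment effect will be diluted. That is conditional: it needs arms that differ in mortality or non-recovery and a non-zero share of such extubations, and the documents supply no share. A reader might go further and expect the worse arm to appear better. Nothing here shows that. In the model above, the recorded difference keeps its sign for every f below 1, and a reversal would need timing assumptions that the documents do not give.

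Third, a rule for deaths could do much of the work. If every patient who dies within follow-up is classed as never liberated, end-of-life extubations followed by death in that period drop out, and date of death is already collected. This stands, so it would be wrong to say that no rule for deaths could help. But the plan has no such rule, and one chosen later would be chosen after the fact.

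Fourth, respiratory support data on Days 1 to 3 and respiratory parameters on Days 7 and 14 could reveal some reintubations. They would reveal some, but not reliably, since a reintubation between those days need not show.

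Finally, this is one of eight secondary endpoints, with no planned test or power, and the 48-hour window proposed below is a convention that the documents do not require. All true; these facts limit the weight of the point without removing it.

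**Conclusion.** The point holds as a gap in endpoint definition and data collection. Followed literally, the plan lets end-of-life and failed extubations supply events for an efficacy endpoint, and failed extubations could not be reliably removed afterwards.

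The size is illustrative. Under the SAP's mortality of 0.50 versus 0.25, with all patients ventilated, 15% per arm alive but still ventilated and the same f in both arms, a 25-point difference is recorded as 20 points at f = 0.2 and 15 points at f = 0.4. Failed extubations would reduce it further under the assumed rate in the working. The bias vanishes if mortality and non-recovery are equal, and it would partly mask harm if the drug raised mortality.

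A reader might take the SAP citation to mean that the planned power is wrong. It is not: the 82% for mortality reproduces and is unaffected. The change should be made, but it does not bear on the primary endpoint.

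**What to change.** In Study Design and Endpoints, replace the bare name with successful liberation: alive and free of invasive ventilation for at least 48 consecutive hours, dated at the start of that period. State that an extubation at withdrawal of life support, or one followed by reintubation within 48 hours, is not an event. Name the time origin in the same place.

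For this endpoint, treat death before liberation as a competing event, or rank it as never liberated, instead of handling it as withdrawal. Without that rule, the endpoint still cannot be analysed in patients who die on the ventilator.

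In the list of additional clinical data, collect every intubation and extubation date and the reason for each extubation, and state how tracheostomy enters the endpoint. Use the same definition at all three sites, since their data are to be analysed together, and settle it before unblinding.

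The cost is endpoint wording, two fields taken from the medical record and slightly fewer events. No treatment or patient management changes.

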# Eligibility

# Inclusion Criteria

In order to be eligible to participate in this study, the patients must meet all of the following criteria:

- At least 18 years of age
- Confirmed COVID-19 disease (by Cobas SARS-CoV-2 real time reverse transcription polymerase chain reaction (RT-PCR) using nasopharyngeal swab sample, or equivalent test available to be performed by the Columbia University Irving Medical Center (CUIMC)/New York Presbyterian (NYP) clinical laboratory). Effort will be made to have the confirmatory test result <72 hours prior to enrollment however given overall clinical demand this may not be feasible in all cases.
- Respiratory failure manifesting as: Acute Respiratory Distress Syndrome (defined by a P/F ratio of <200), OR oxygen saturation (SpO2) < 90% on 4 liters (L) (actual or expected given higher O2 requirement) OR increasing O2 requirements over 24 hours, plus 2 or more of the following predictors for severe disease:

- CRP > 35 mg/L Ferritin > 500 ng/mL D-dimer > 1 mcg/L Neutrophil-Lymphocyte Ratio > 4 Lactate dehydrogenase (LDH) > 200 U/L Increase in troponin in patient w/out known cardiac disease
- Has a consent designee willing to provide informed consent on behalf of the patient (this
  assumes that a mechanically ventilated patients lacks capacity to consent on his/her own behalf.
  Should it be deemed that the patient has capacity to consent, consent may be obtained from
  the patient.)
- Women of childbearing potential must be willing and able to use at least one highly effective contraceptive method for a period of 5 months following the study drug administration. In the context of this study, an effective method is defined as those which result in low failure rate (i.e. less than 1% per year) when used consistently and correctly such as:
  - combined (estrogen and progestogen containing) hormonal contraception combined (estrogen and progestogen containing) hormonal contraception (oral, intravaginal, or transdermal)
  - progestogen-only hormonal contraception associated with inhibition of ovulation (oral, injectable, implantable)
  - intrauterine device (IUD)
  - intrauterine hormone-releasing system (IUS)
  - vasectomized partner
  - o bilateral tubal occlusion
  - true abstinence. when this is in line with the preferred and usual lifestyle of the subject.
     Periodic abstinence, such as calendar, ovulation, symptothermal, postovulation methods, and withdrawal are not acceptable methods of contraception.

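### Time to extubation, RRT duration and possibly ICU stay are defined only for patients who have the event; comparing arms in those subsets is not protected by randomisation and can hide or reverse a benefit

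*Combined protocol and SAP*

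**What the plan says.** The secondary objective (Objectives and Purpose) concerns efficacy and is worded as "evaluating the incidence and duration of mechanical ventilation, the length of ICU stay, severity and duration of acute kidney injury (AKI) and patient survival". Study Design and Endpoints turns this into "incidence of intubation, time to extubation, length of ICU stay", then a CRP trend, then "severity of AKI, need for RRT, duration of RRT, and patient survival at 28 and 60 days". Intubation and RRT are thus outcomes in their own right, and the durations of the same two supports are separate outcomes.

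The Inclusion Criteria admit patients by ARDS, by low saturation on low-flow oxygen, or by "OR increasing O2 requirements over 24 hours, plus 2 or more of the following predictors for severe disease". None of these routes requires ventilation, ICU care or RRT at entry. The same section also expects some patients to be ventilated already: its consent item "assumes that a mechanically ventilated patients lacks capacity to consent on his/her own behalf". Strategies for Recruitment and Retention describes recruits as critically ill, and Participant Withdrawal or Termination expects them to be probably in an ICU for the 14-day data period. No section gives the share ventilated, in ICU or on RRT at baseline.

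The list of additional clinical data after the schedule of events records intubation, extubation and RRT dates only where the procedure takes place. It includes a date of ICU discharge but no date of ICU admission. The SAP covers descriptive safety statistics, confidence interval widths for SAE rates, and power for mortality. For the three durations it gives no time origin, population, value for patients without the event, rule for death, or method.

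**The concern.** A never-intubated patient has no time to extubation, and a patient never dialysed has no RRT duration. Length of ICU stay behaves the same way if patients never admitted are left out. If the endpoints are analysed as named, each arm contributes only its patients with the event, and the drug is meant to change who those patients are. The two subsets need not be alike even under perfect randomisation.

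The direction matters. If the drug spares the milder candidates for intubation, those who remain on the drug arm are the sicker ones, with longer courses. The duration endpoint can then show no difference, or a longer time on support, although the arm as a whole used less. Incidence of intubation and need for RRT would still show part of the benefit, but the report could carry two secondary results pointing in opposite directions with no prior rule for reading them. The data are to be pooled over three sites, so a shared definition is needed before unblinding.

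**Working it through.** **The plan's own figure.** The text gives one power figure, for mortality: about 82% for 0.50 v 0.25 with 60 per arm, two-sided alpha 0.05. With p̄ = 0.375, SE0 = √(2 × 0.375 × 0.625 / 60) = 0.0884 and SE1 = √((0.25 + 0.1875) / 60) = 0.0854. Power = Φ((0.25 − 1.96 × 0.0884) / 0.0854) = Φ(0.90) = 81.6%. It reproduces, but says nothing about the durations. Every input below is therefore an assumption; none is in the documents.

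**Three records.** Placebo: never intubated, 3 days, 20 days. The drug spares the 3-day patient.
- Mean among the intubated: (3 + 20) / 2 = 11.5 days on placebo v 20 on drug.
- Mean over all three, 0 if never intubated: 23 / 3 = 7.7 v 20 / 3 = 6.7 days.

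The first comparison favours placebo, the second the drug.

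**Dependence on baseline status.** Let a share b already have the event at entry (18 days in either arm). Of the rest, 30% are severe (event in either arm, 18 days), 20% mild (8 days, prevented by the drug) and 50% never have it. There are no deaths and no effect on duration.
- Placebo mean among patients with the event: [18b + (1 − b)(0.3 × 18 + 0.2 × 8)] / [b + 0.5(1 − b)].
- Drug mean among patients with the event: 18 for every b.
- All randomised, 0 if no event: 18b + 7.0(1 − b) on placebo, 18b + 5.4(1 − b) on drug.
- True shortening that cancels the gap: 1 − placebo mean / 18.

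| b | With the event, placebo v drug (days) | Gap (days) | Cancelling shortening | All randomised, placebo v drug (days) |
|---|---|---|---|---|
| 0 | 14.0 v 18.0 | +4.0 | 22% | 7.0 v 5.4 |
| 0.25 | 15.6 v 18.0 | +2.4 | 13% | 9.75 v 8.55 |
| 0.50 | 16.7 v 18.0 | +1.3 | 7% | 12.5 v 11.7 |
| 0.75 | 17.4 v 18.0 | +0.6 | 3% | 15.25 v 14.85 |
| 0.90 | 17.8 v 18.0 | +0.2 | 1% | 16.9 v 16.7 |

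A shortening above the cancelling value makes the restricted comparison favour the drug.

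**A continuous version.** Severity S ~ N(0,1); the most severe are intubated, 50% on placebo and 30% on drug; duration = exp(ln 8 + k(S − 0.8) + 0.6e), with e ~ N(0,1); no deaths. Median days among the intubated, placebo v drug:
- Nobody ventilated at entry: 8.0 v 8.0 (k = 0), 8.0 v 9.2 (k = 0.4), 7.7 v 10.4 (k = 0.8). At 60 per arm the drug median is the longer in 73% (k = 0.4) and 86% (k = 0.8) of simulated trials, against 50% by chance.
- Half ventilated at entry (the most severe), the rest intubated 50% v 30%: about 6.8 v 7.2 (k = 0.4) and 5.7 v 6.4 (k = 0.8).
- Ventilator days to Day 28 over all patients, nobody ventilated at entry: 4.7 v 2.8, 4.8 v 3.3 and 5.0 v 3.8 for k = 0, 0.4 and 0.8. They favour the drug throughout. At k = 0 the restricted median misses that benefit.

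**Deaths.** Participant Withdrawal or Termination puts predicted mortality in COVID-19 ARDS above 50% and treats death as withdrawal. If early death cuts the severe course to 6 days (b = 0), the means become (0.3 × 6 + 0.2 × 8) / 0.5 = 6.8 on placebo v 6.0 on drug, and the sign reverses.

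Death also decides which replacement is safe. Let half be intubated in both arms, all deaths fall among the intubated after a mean of 4.8 ventilator days, and intubated survivors need 8 days. Cut mortality from 50% to 25%:
- Plain ventilator days: 0.50 × 4.8 = 2.4 v 0.25 × 4.8 + 0.25 × 8 = 3.2. The life-saving drug looks worse.
- Ventilator-free days to Day 28, death scored 0: 0.50 × 28 = 14.0 v 0.50 × 28 + 0.25 × (28 − 8) = 19.0. The drug looks better.

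**The case against.** The strongest reply is that the plan never says the analysis will be restricted to patients with the event. It lists endpoint names; the conditional wording in the data list describes data capture, not an analysis set; and ICU stay can be scored 0 for a patient never admitted. That stands as far as it goes: a reader might infer that a biased analysis has been chosen, and the documents do not show this. But time to extubation and duration of RRT have no natural value without the event, and nothing in the SAP supplies one.

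A reader might also infer that most of these events follow randomisation. The documents do not support that. No baseline share is given, and the consent item, the recruitment text and the expected ICU setting all suggest that many patients are already ventilated or in ICU. This shrinks the bias, as the table shows, without removing it.

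Nor do the documents support the reading that an effective drug will appear to lengthen all three durations. That needs a restricted analysis, enough events after randomisation, shorter courses in milder cases, and neither a true shortening nor truncation by death large enough to offset it. With k = 0 there is no lengthening at all.

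A false significant result against the drug is also not the typical outcome. In the continuous model with 60 per arm, a Wilcoxon test is significantly against the drug in roughly 10% to 25% of trials with nobody ventilated at entry, and in fewer than 10% with half ventilated. The usual harm is a masked or contradictory result.

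**Conclusion.** The point holds in a limited form. As named, time to extubation and duration of RRT, and length of ICU stay if patients never admitted are left out, compare subsets selected by outcomes that the drug is meant to change. The comparison is not protected by randomisation and can hide a benefit or point against a drug that prevents milder events.

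Under the assumed mixture the apparent lengthening runs from 4.0 days (nobody with the event at entry) to 0.2 days (90% with it). The size rests on the unstated baseline share, the link between severity and duration, any true shortening and deaths; the last two can reverse the sign. The case is clearest for extubation and RRT and weakest for ICU stay. These are secondary endpoints in a trial whose primary endpoint is safety, so the change should be made, but the point does not threaten the primary analysis.

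**What to change.** In Study Design and Endpoints and in the SAP:
- Compare the arms on ventilator-free, ICU-free and RRT-free days from Day 1 to Day 28 in all randomised patients. Score a survivor who never has the event as 28 and a patient who dies by Day 28 as 0.
- Report durations among patients with the event as descriptive only, with no comparison between arms.
- Report ventilation, ICU and RRT status at baseline by arm.
- Add date of ICU admission to the list of additional clinical data.

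The cost is endpoint and SAP wording, to be shared by the three sites before unblinding, plus one date field. Intubation, extubation and RRT dates and Day 28 survival are already collected. The downside is that the measure combines incidence, duration and death, so it is less direct to explain than time to extubation. Incidence of intubation, need for RRT and survival remain as separate endpoints and help to show which component drives a difference.
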